#### 6.3.5 Specimen Processing Procedures

#### 6.4 Suspension and withdrawal

Patients who were screened and confirmed to be eligible for the study, signed the informed consent and completed the randomization were considered as enrolled. If serious program deviation, withdrawal, or death occurs, the subject study is considered to be suspended. If the subject discontinues the study after obtaining informed consent, the data before the discontinuation will still be included in the study-related analysis.

##### 6.4.1 Pre-Procedure

In any time during the study period, even before Colonoscopy, participants could withdraw their informed consent whenever necessary. Researchers can withdraw participants before surgery according to safety considerations in the inclusion and exclusion criteria.

##### 6.4.2 Intraprocedure

For safety reasons, the investigator may have the subject quit during the procedure. For example, the patient is not suitable for receiving the instrument for the study or the endoscopists do not use the specified instrument for any reason. If the following serious

cases occur, please withdraw during the operation:

- a) perforation
- b) bleeding
- c) allergy to narcotic drugs
- d) Intestinal cleanliness is very poor, endoscopic physicians can not smoothly advance: a single intestinal segment is less than 1 point
- e) can not complete colonoscopy due to obstruction, intolerance, inflammatory bowel disease or colorectal resection
- f) can not biopsy due to coagulation dysfunction or oral anticoagulants

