## **4 Endpoints**

### **4.1 Primary Endpoint**

- 1) CUSUM learning curve for colonoscopy (ACE scoring scale)
- 2) Average test score difference before and after training

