- 9) The average number of adenomas detected in different sites: the numerator is the total number of adenomas detected in the rectum, sigmoid colon, descending colon, transverse colon, ascending colon, ileocecal region and other sites during colonoscopy, and the denominator is the total number of patients undergoing colonoscopy.
- 10) Number of missed return of the sliding endoscopy/number of successful return of the sliding endoscopy: the numerator is the total number of sliding endoscopy during colonoscopy, and the denominator is the number of sliding endoscopy and successful return endoscopy during colonoscopy
- 11) Real-time gut cleanliness score: during colonoscopy, a real-time intestinal cleanliness score was given by EndoAngel based on the Boston-scale Boreal Preparation Score (BBPS).

- 12) withdraw overspeed percentage:the ratio of the overspeed duration to the total duration in the process of withdrawal.
- 13) The withdraw time:the time between colonoscopy arrival at ileocecal valve and colonoscopy exit from anus.
- 14) Ratio of ileocecal reach:for a period of time, the number of colonoscopies that failed to reach the ileocecal part accounted for the proportion of the total number of colonoscopies.

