### **6.3.3 Intraoperative Managements**

- 1) Patient position: prone position with appropriate restraint.
- 2) Insertion route: according to the actual situation of the subject, usually through the anus
- 3) Patients in the control group received colonoscopy without AI assistance, and patients in the experimental group received colonoscopy with AI assistance. The advanced physician carries on the colonoscopy examination under the teacher's guidance.
- 4) After the examination, the teacher scored the colonoscopy according to the ACE scoring scale.

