#### **6.4.2 Replacement**

Subject will be deemed to have commenced the study upon completion of the informed consent process, and any subject who has been discontinued prior to or during the Colonoscopy will not subsequently be replaced by other subjects

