### 8.3 Sample Size Calculation

The main evaluation focus of this project plan is to evaluate whether there is a significant difference in ACE scores of colonoscopy training for endoscopic physicians by using EndoAngel. This project plans to carry out clinical trials in 3 hospitals. According to the literature, we assume that the cognitive score of endoscopists can be increased from 2.5 to 2.8 after intervention, then 126 cases of colonoscopy need to be enrolled, and if the motor score of endoscopists is increased from 2.38 to 2.59, then 350 cases need to be enrolled. Considering the experimental abscission rate of 10%, a total of 385 cases of colonoscopy should be included.

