### 8.4 Statistical analysis set

All patients who met the inclusion and exclusion criteria were considered eligible for recruitment.

The two analysis sets in this study are defined as follows:

- The full analysis set (FAS) population analysis set will contain all eligible cases and shedding cases, but does not include culling cases.
- The Compliance (PP) population analysis set will include all subjects in the FAS analysis set with no significant deviation from the program.

Intention-to-treat and conformity analysis sets should be used to analyze the primary efficacy endpoints. The main analysis will be based on the PP analysis set. FAS analysis was regarded as supportive analysis.

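### Section 6.4.2 (Intraprocedure) permits withdrawal of a randomised case because the specified instrument was not used, so the case may have no ACE score or fall outside the per-protocol main analysis

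*Combined protocol and SAP*

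**What the plan says.** - **Timing and arms.** Under section 6.5.1, randomisation comes before colonoscopy and decides whether EndoAngel is used. Section 6.3.3 gives AI assistance to the experimental group only.
- **Withdrawal.** Section 6.4.2 (Intraprocedure) permits the investigator to withdraw a subject during the procedure. The permission is introduced as a safety measure, and one example is that "the endoscopists do not use the specified instrument for any reason". A separate list, a to f (perforation, bleeding and so on), directs withdrawal. Non-use of the instrument is not on that list.
- **Software failure.** Section 7.5 says that doctors can go on under their own judgment if the software has faults.
- **Scoring.** Section 6.3.3: "After the examination, the teacher scored the colonoscopy according to the ACE scoring scale".
- **Data and replacement.** For a subject who discontinues, section 6.4 says "the data before the discontinuation will still be included in the study-related analysis". It is silent on anything recorded later. Section 6.4.2 (Replacement) adds that "any subject who has been discontinued prior to or during the Colonoscopy will not subsequently be replaced by other subjects".
- **Analysis sets.** Section 8.4: "The main analysis will be based on the PP analysis set". That set is the FAS less subjects with a significant deviation, and the FAS itself omits culling cases. Neither term is defined. The FAS analysis is supportive.
- **Outcome.** Section 8.3 gives the main focus as being to "evaluate whether there is a significant difference in ACE scores of colonoscopy training". The primary endpoints in section 4.1 are the CUSUM learning curve on ACE and "Average test score difference before and after training".

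**The concern.** Withdrawal under this example happens after randomisation, while the AI prompts are on view and the trainee's performance so far can be seen. Not running advisory software is not in itself a danger to the patient, since section 7.5 lets the examination go on without it. Yet the example, as worded, covers non-use on any ground.

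The case can then drop out of the ACE comparison in two ways. If it is stopped before the end, it may never be scored. If it is finished and scored, non-use may be judged a significant deviation and the case left out of the main analysis.

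Only the experimental arm is assigned AI assistance, so the trigger probably bears mainly on that arm. If teachers or trainees tend to abandon the system when an examination is going badly, low-scoring AI cases leave while comparable control cases stay, and the AI mean rises for reasons unrelated to training. The affected data are those on which the trial was sized. The before/after test score is not directly removed by withdrawing a patient case.

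**Working it through.** **1. The plan's own figure.** Section 8.3 takes 350 cases for a motor ACE score rising from 2.38 to 2.59 (difference 0.21) and adds 10%: 350 × 1.10 = 385, which reproduces. The plan states no SD, alpha or power. Assuming 175 per arm, two-sided 5% and 80% power, the implied SD is 0.21 / (1.960 + 0.842) × √(175/2) = 0.701. I use 0.70 below and treat cases as independent. Both are assumptions.

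**2. Following one case through the text.** An AI case is randomised and EndoAngel is not used or is switched off.
- Withdrawn mid-procedure: ACE comes after the examination, so there may be no score. Section 6.4 promises only earlier data, and the case is not replaced.
- Finished and scored: it stays in the FAS unless culled, but leaves the per-protocol set if non-use counts as a significant deviation.

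Either way it can be missing from the main ACE analysis.

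**3. Size of a false difference when EndoAngel has no effect.** Let a share p of AI cases and q of control cases be excluded, each scoring g points below the retained cases of their arm. With equal true means, retained AI minus retained control = (p − q) × g. The standard error is 0.70 × √(1/[175(1 − p)] + 1/[175(1 − q)]). With b the false difference divided by that standard error, type I error = Φ(b − 1.96) + Φ(−b − 1.96).

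| p (AI) | q (control) | g | False difference | Type I error |
|---|---|---|---|---|
| 2% | 0 | 0.5 | 0.010 | 5.2% |
| 2% | 0 | 1.0 | 0.020 | 5.8% |
| 5% | 0 | 0.5 | 0.025 | 6.3% |
| 5% | 0 | 1.0 | 0.050 | 10.1% |
| 5% | 2.5% | 0.5 | 0.0125 | 5.3% |
| 5% | 2.5% | 1.0 | 0.025 | 6.2% |
| 5% | 5% | 0.5 or 1.0 | 0 | 5.0% |

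For the fourth row: standard error 0.0758, b = 0.050 / 0.0758 = 0.66. All values of p, q and g are assumed, because the documents give no non-use rate and no scores for such cases. The table concerns the mean motor ACE difference. The CUSUM curve cannot be computed because the plan gives no target or step.

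**4. Price of keeping the cases as randomised.** Suppose hard cases occur alike in both arms and non-use simply forfeits the benefit. At 5% non-use the difference is 0.95 × 0.21 = 0.1995, whatever those cases score.
- 175 per arm: standard error 0.70 × √(2/175) = 0.0748. Power is Φ(0.21/0.0748 − 1.96) = 80.1% without non-use and Φ(0.1995/0.0748 − 1.96) = 76.0% with it.
- All 385 scored (192 and 193): standard error 0.0714. Power is 83.7% and 79.8%.
- Restoring 80% power at a difference of 0.1995 takes 388 evaluable cases instead of 350.

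**The case against.** The strongest reply is that the harm needs a chain of conditions. The investigator must use a discretion that the section introduces as a safety measure. The instrument must be EndoAngel. The score must be missing, or a significant deviation declared. Non-use must go with poor performance, and it must differ by arm. The documents do not establish the last three.

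Much of this stands:
- **The instrument is not identified.** The same sentence of 6.4.2 mentions patients unsuited to receiving it, an odd fit for software that section 7.4 describes as not touching the body. It could include the endoscope used in both arms. Even EndoAngel may run silently in controls: section 4.2 says that "a real-time intestinal cleanliness score was given by EndoAngel", without limiting this to an arm, and section 6.3.4 collects images and video for its evaluation in the same unrestricted way.
- **The examination need not stop.** Section 7.5 points to carrying on, and section 6.3.3 makes no exception to scoring.
- **Barring replacement is sound practice** in a randomised trial and is no fault here.
- **The per-protocol main analysis is a wider matter.** For finished, scored cases, correcting section 8.4 alone would suffice. It would not help a case that was stopped and never scored, so the wording of 6.4.2 still matters.

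A reader might infer that the plan orders AI cases to be dropped, or that the result is bound to favour EndoAngel. Neither is supported: the rule is permissive, and the direction depends on facts not given. Nor is a withdrawn case necessarily lost everywhere, since the FAS keeps shedding cases.

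A reader might also infer that the remedy is expensive. Giving non-use cases a score of 1.5 in the AI arm alone yields 0.95 × 2.59 + 0.05 × 1.5 − 2.38 = 0.1555, with power of 54.7% and 638 cases needed. A score of 1.88 gives 0.1745, 64.5% and 506. Those figures hold only if non-use itself pushes scores below control.

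**Conclusion.** The point holds as a gap in the rules, with medium confidence, and should be fixed. The plan allows a post-randomisation event that is not itself a safety ground, and that probably arises mainly in the AI arm, to remove cases from the main ACE analysis. Whether this biases the result is unknown. Bias towards EndoAngel requires non-use that is both linked to poor performance and unequal between arms. If non-use is unrelated to performance, or if rates and score gaps match across arms, there is no false difference under no effect.

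At 2% non-use the effect is small on these assumptions. The 10.1% figure needs 5% non-use, none in controls, and a gap of a full ACE point (about 1.4 of the assumed SDs). The identity of the instrument and the arm imbalance are inferences. Stopping rules a to f are not in question.

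**What to change.** **Section 6.4.2 (Intraprocedure).** Delete non-use of the instrument as a withdrawal example, keep a to f, and add: *Non-use, failure or switching off of EndoAngel in an experimental case, or AI prompts shown in a control case, is not a reason to withdraw. The examination continues if clinically appropriate, the teacher completes the ACE score, and the event, its time and its reason are logged.*

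**Section 8.4.** Add: *These cases are never culling cases and stay in the FAS in their randomised arm. For the ACE endpoint the as-randomised FAS analysis is the main analysis. The PP analysis, which may exclude these cases, is supportive.*

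Both edits are needed: the first secures the score and the second settles where it is analysed.

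**Cost.** Two wording changes, one CRF field and modest dilution. At 5% non-use that only forfeits the benefit, the difference falls from 0.21 to about 0.20. Power falls from about 80% to 76% with 175 per arm, or from about 84% to 80% if all 385 cases are scored. Excluding 5% of AI cases instead would keep about 79% power with 175 per arm, but would leave the comparison open to the selection described above. No safety protection is removed.

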#### **6.4.2 Replacement**

Subject will be deemed to have commenced the study upon completion of the informed consent process, and any subject who has been discontinued prior to or during the Colonoscopy will not subsequently be replaced by other subjects

### **6.5 Randomization and Blinding**

#### **6.5.1 Randomization Implementation**

Randomization is conducted according to the study protocol, and the random contents are implemented in an electronic system block-randomized manner (n = 4; experimental group/control group = 1). Randomization prior to Colonoscopy to decide whether to use EndoAngel. The researchers randomized the random results generated by the electronic system, and the generated random results were stored in the research center. The random time (accurate to minute), random person, subject number and acronym were recorded in the corresponding positions of the electronic system.

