Study Process:	
1. Subjects meeting all inclusion criteria and those failing all exclusion criteria were included in the study before colonoscopy;
 
2. Include qualified novice doctors for colonoscopy training
 
3. Patients who met the requirements were enrolled and randomly assigned as follows
 
The experimental group: received painless colonoscopy training with the assistance of the artificial intelligence assistant system, which could prompt abnormal lesions and real-time withdrawal speed, and feedback the overspeed percentage.
 
Control group: routine painless enteroscopy training, no special tips.
 
4. After colonoscopy, the teacher scored the colonoscopy using ACE scoring scale

Security	Safety incidents shall be evaluated and reported according to the quality management measures for clinical trials of medical devices

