#### 3.1 Endoscopic physician

➤ Inclusion criteria

Novice colonoscopists without previous experience in independent colonoscopy;

➤ Exclusion criteria

- 1) The number of operating cases does not meet the requirement of sample size
- 2) could not provide informed consent

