### **3.3 Definition of enrollment**

After participants signed informed consent, they were randomized before colonoscopy. The randomization time was the enrollment time, and was recorded in CRF.

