#### **6.5.2 Blinding Implementation and Protection**

Subjects and evaluators are blinded according to the protocol.

Randomization results will be kept confidential to the subjects in general. Randomization results are not reflected in inpatient history and other subject access documents. During and after the examination, study personnel should take care not to talk to the subject about the results of the randomization to avoid unnecessary unblinding

The assessors are blinded, and the data analysis team and pathologists could not obtain the randomization results from the medical history data.

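### A printed fixed block of 4, with no strata and arms visible to operators, lets up to one third of allocations be deduced where the full sequence is seen, and leaves trainee balance to chance with no adjustment

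*Combined protocol and SAP*

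**What the plan says.** Section 6.5.1 allocates through an electronic system in a "block-randomized manner (n = 4; experimental group/control group = 1", that is, 1:1 in blocks of 4. Researchers carry out the randomisation, and "the generated random results were stored in the research center". The section does not mention varying block sizes, withholding the block size from sites, strata, or whether there is one common list or one per hospital. Section 8.3 states "This project plans to carry out clinical trials in 3 hospitals".

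The randomised unit appears to be the patient. Section 3.3 says "After participants signed informed consent, they were randomized before colonoscopy", and the summary in section 1 says "Patients who met the requirements were enrolled and randomly assigned as follows". The operators are described in section 3.1 as "Novice colonoscopists without previous experience in independent colonoscopy"; their number is not given.

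On blinding, section 6.5.2 says "Subjects and evaluators are blinded according to the protocol" and adds the data analysis team and the pathologists. It names neither trainees as operators nor teachers. In the experimental arm the trainee works with a system "which could prompt abnormal lesions and real-time withdrawal speed" (section 1), and the teacher guides the examination (section 6.3.3).

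Section 8.2 gives descriptive summaries, correlations and a chi-square analysis. It names no model for the ACE scores, and so no term for hospital or trainee.

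**The concern.** An electronic system hides the list but not the pattern. Anyone who knows that blocks have length 4, knows where a block starts and has seen its earlier allocations can work out the rest once two cases in it have gone to the same arm. The block length is in the protocol. The people in the room learn each allocation when the prompts appear or fail to appear, and the researcher who randomises also sees the result.

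Foreknowledge matters because some judgement comes before randomisation. Inclusion criterion 3 and exclusion criterion 10 in section 3.2 rest on the investigator's opinion, and consent precedes allocation. If an expected arm influenced who was entered or when, easier or harder examinations could collect in one arm. Section 6.5.3 itself recognises that revealing one subject's allocation can reveal others and harm the analysis.

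The second issue is precision. With no strata and no model terms, differences between hospitals or trainees in ACE scoring enter the arm comparison as noise. The effects assumed in section 8.3 are small: 0.30 points on the cognitive score and 0.21 on the motor score.

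**Working it through.** **Plan's own figure.** Section 8.3: 350 × 1.10 = 385. This reproduces and is used below as the number of allocations.

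**1. Observer who sees every allocation and knows the block boundaries (fixed block of 4, 1:1).** There are 6 equally likely orders of two experimental and two control cases.
- Certain: positions 1 and 2 never; position 3 when the first two match, probability 1/3; position 4 always. Share = (0 + 0 + 1/3 + 1)/4 = 1/3 (8 of 24 positions). In 385 cases there are 96 full blocks, and 96 × 4/3 = 128.
- Best guess right: 1/2, 2/3, 2/3 and 1 at the four positions. Mean = (17/6)/4 = 17/24 = 70.8%, against 50% with no predictability.

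**2. One common list, observer sees only their own hospital.** Assume 3 hospitals with equal random arrival, and list positions known.
- Certain at position 3: both earlier cases at the own site (1/9) and matching (1/3) = 1/27. At position 4: the matching pair among the first three both at the own site = 1/9. Share = (1/27 + 1/9)/4 = 1/27 = 3.7%.
- Best guess right: 13.5/27, 15/27, 16/27 and 17/27 at the four positions. Mean = 61.5/108 = 56.9%. Simulation gave the same two values.

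**3. Chance imbalance.** With blocks of 4 on a list of N cases and a unit receiving each case with probability p, the variance of the difference in arm counts within that unit is about N·p·(1 − p). The mean absolute difference is about 0.80 × SD, and the 95th percentile about 1.96 × SD. The number of trainees is not documented; 6 to 12 is assumed.

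| Unit, on one common list (N = 385) | Variance | SD | Mean difference | 95th percentile |
|---|---|---|---|---|
| Hospital, p = 1/3 | 385 × 2/9 = 85.6 | 9.2 | 7 of about 128 | 18 |
| Trainee, 6 in all, p = 1/6 | 385 × 5/36 = 53.5 | 7.3 | 6 of about 64 | 14 |
| Trainee, 12 in all, p = 1/12 | 385 × 11/144 = 29.4 | 5.4 | 4 of about 32 | 11 |

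Simulation agrees. With a separate list per hospital, the hospital difference is at most 2. The trainee difference is little changed: with 2 trainees per hospital, 128 × 1/4 = 32, SD 5.7, mean about 4.5.

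**4. Effect of varying the block size (full sequence visible, set of sizes known).**

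| Blocks | Certain | Best guess right |
|---|---|---|
| Fixed 4 | 33.3% | 70.8% |
| Random 4 and 6 | about 5.3% | about 69.3% |
| Random 4, 6 and 8 | about 2.3% | about 68.0% |

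The mixed rows are simulated. Varying the blocks removes nearly all certainty but little of the guessing advantage.

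**The case against.** The strongest reply is that the one-third figure is conditional. It needs someone who sees every allocation in the block and knows its boundaries. On one common list, an own-site observer is certain in only 3.7% of cases. The two consequences also depend largely on opposite list structures: lists per hospital make prediction easy but keep each hospital within 2, while a common list leaves hospital balance to chance but makes prediction hard. This stands, and it is why the size must be given as a range. The trainee issue remains under either structure.

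A reader might infer that hospital and trainee are unbalanced by design. They are not: patient-level 1:1 randomisation balances both in expectation, and the chance differences are moderate.

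A reader might also infer that trainees are the main source of variation in ACE scores, or that staff choose which consented patient a trainee sees next. The documents give no variance component and describe no such choice. Section 6.5.1 also has the time of randomisation, to the minute, and the person randomising recorded, which gives an audit trail. Steering is therefore a possibility, not something shown.

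That the teacher sees the arm is an inference from the teacher's role in guiding the case. How this fits with blinded evaluators, given that the teacher also scores ACE, is a separate question.

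**Conclusion.** The point holds as an avoidable weakness that is cheap to correct. The protocol discloses a fixed block of 4, operators see the arm, and neither list structure nor strata are stated. Between about 4% of allocations (one common list, own-site view, equal random arrival) and 33% (full sequence visible) could be known in advance; the best-guess rate runs from 57% to 71%. Balance by trainee, and by hospital under a common list, is left to chance, and no adjustment is planned.

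The predictability figures assume that patients are the randomised unit, as sections 1 and 3.3 indicate, and that the observer knows the block boundaries or list positions. The trainee figures assume 6 to 12 trainees with equal caseloads. The documents do not support saying that one third of allocations are predictable without condition, or that the arms will be unbalanced.

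**What to change.** 1. In section 6.5.1, state that patients are the randomised unit (or correct this if they are not) and that there is one list per hospital.
2. Set the electronic system to randomly varying block sizes, for example 4, 6 and 8, within hospital strata. Move the sizes to a restricted document and out of site-facing text.
3. In section 8.2, specify a model for the ACE scores with hospital and trainee as terms. If each trainee works in one hospital, trainee can be a random effect within hospital.
4. Do not stratify by trainee with small blocks. That would give each trainee and teacher a short list that they see in full; model adjustment deals with trainee without this cost.

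The gain is that certain allocations fall from up to 33% to about 2–3%. The best-guess rate falls only from 71% to about 68%, so the change should not be presented as making allocation unpredictable.

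The cost is a system setting and a few sentences. There are two downsides. The possible end-of-list imbalance is slightly larger: up to 4 per hospital with a largest block of 8, against 2 with blocks of 4. Lists per hospital are also easier to guess at the site than one common list (about 68% against 57% for an own-site observer), which is the price of guaranteed hospital balance. If the sponsor prefers a common list, it should say so and rely on the model term for hospital.

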Based on the above rich foundation of preliminary work and the huge demand in the field of colonoscopy training, we intend to train beginners in colonoscopy operation by comparing the cases of EndolAngel assistance and no EndolAngel assistance. To explore whether AI can promote the training of colonoscopy for beginners.

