### 3 Selection

The subjects in this study were divided into endoscopists and colonoscopy patients. The endoscopists were required to be beginners without independent experience in colonoscopy, and the colonoscopy patients were male or female  $\geq 50$  years old who needed to undergo colonoscopy screening, volunteered to provide endoscopic imaging data and signed informed consent, and such patients were included in the study. 50 years of age is the recommended age for the first colonoscopy screening, so the investigation of subjects  $\geq 50$  years of age can better represent the quality of the colonoscopy test population.

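### EndoAngel is randomised by patient, and no readable text allocates trainees, so the before/after test score has no documented randomised comparison of AI with no AI

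*Combined protocol and SAP*

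**What the plan says.** **Unit of allocation.** Section 1 (Study Process) states: "Patients who met the requirements were enrolled and randomly assigned as follows". Section 3.3 says of participants who have consented that "they were randomized before colonoscopy". Section 6.1 randomises the enrolled patient, section 6.3.3 attaches the arms to patients, and section 6.4 counts patients as enrolled once randomisation is complete. Section 6.5.1 describes the step as "Randomization prior to Colonoscopy to decide whether to use EndoAngel", 1:1 in blocks of 4, and names no trainee stratum or cluster.

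**Trainees.** Section 3 says: "The subjects in this study were divided into endoscopists and colonoscopy patients". Section 1 lists the inclusion of novice doctors as a step of its own, and section 6.2.3 gives endoscopists their own number series. Section 1 also describes the experimental group as one that "received painless colonoscopy training with the assistance of the artificial intelligence assistant system".

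**Aim and endpoints.** Section 5.1 asks whether EndoAngel helps in training beginners. The primary endpoints in section 4.1 are a CUSUM learning curve on the ACE scale and "Average test score difference before and after training". Under section 6.3.3 the teacher gives an ACE score after each examination. Section 8.3 treats the ACE difference as the chief object of evaluation and counts colonoscopies. Section 8.2 gives no arm comparison for either primary endpoint.

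**The concern.** The question is about trainees, but the randomisation is of patients. A randomised comparison protects only what is measured on the randomised unit, or on something nested within it. An ACE score belongs to one colonoscopy and so to one randomised patient. A before/after test change, on the natural reading, belongs to a trainee who performs many colonoscopies.

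At stake is the central claim. A difference in test scores would probably be read as evidence that AI improves training, yet the plan documents no randomisation that would support that reading. More patients would not cure this, because the gap is in what was allocated and not in precision.

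**Working it through.** **Step 1: who is randomised, section by section.**

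| Section | Unit named |
|---|---|
| 1, Study Process | Patient |
| 6.1 | Patient |
| 6.3.3 | Patient (arm label) |
| 6.4 | Patient |
| 3.3 | Participant (neutral word) |
| 6.5.1 | Not named; decided before colonoscopy, subject number recorded |

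No readable section names the trainee. The flow chart in section 1.2 is not shown and could not be checked.

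**Step 2: what follows for the test score.** The documents do not say how patients are matched to trainees, so both possibilities need checking.

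- *Matching ignores arm.* With 1:1 allocation, the chance that a trainee with n cases stays in one arm is about 2 × 0.5^n. For n = 10 this is 2 × 0.5^10 = 0.00195, about 0.2%. Nearly every trainee then works in both arms, and a single before/after change belongs to neither.
- *Trainees are kept in one arm.* There is no mixing, but no readable text randomises them to that arm. Differences between trainees or between hospitals could then explain the result.

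In both cases the test score has no documented randomised contrast.

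**Step 3: what the planned size covers.** Section 8.3 gives motor scores of 2.38 and 2.59 (difference 0.21, 350 cases), cognitive scores of 2.5 and 2.8 (difference 0.30, 126 cases), and 10% loss. The last step reproduces: 350 × 1.10 = 385. The 350 and 126 cannot be derived from the text, because no SD, alpha or power is given. Assuming two-sided 5% and 80% power, n per arm = 2(1.96 + 0.84)² SD² / difference²:

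- motor, SD 0.70: 174.4, rounded up to 175 per arm, 350 in total;
- cognitive, SD 0.60: 62.8, rounded up to 63 per arm, 126 in total.

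These SDs are back-solved, so the match is not evidence for them. It shows only that the size is consistent with comparing independent colonoscopies by arm. It counts no trainees.

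**Step 4: illustration if trainees were randomised instead.** Assumed: K = 6 or 20 trainees, SD 0.70, two-sided 5%, 350 cases. The design effect is DE = 1 + (350/K − 1) × ICC. The noncentrality is 0.21 / (0.70 × √(2·DE/175)), on K − 2 degrees of freedom.

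| K | ICC | DE | 350/DE | Power |
|---|---|---|---|---|
| 6 | 0.01 | 1.57 | 222 | 40% |
| 6 | 0.05 | 3.87 | 91 | 20% |
| 6 | 0.10 | 6.73 | 52 | 13% |
| 20 | 0.01 | 1.17 | 300 | 69% |
| 20 | 0.05 | 1.83 | 192 | 50% |
| 20 | 0.10 | 2.65 | 132 | 37% |

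Fitting three hospitals as fixed effects leaves K − 4 degrees of freedom. With 6 trainees and ICC 0.05, power then falls from 20% to 14%.

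**The case against.** The strongest reply is that trainee arms may be intended. Section 1 describes the arms as kinds of training, section 3 counts endoscopists as subjects, sections 3.3 and 6.5.1 use neutral words, and the missing flow chart might show the allocation. This stands as a reason to ask. It does not supply a randomisation of trainees: the training wording sits directly under the sentence that assigns patients.

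A second reply is that section 8.3 puts the weight on ACE and sizes the trial on colonoscopies, so the main comparison survives. That is correct, and it limits the point. A reader might infer that the whole trial lacks a randomised comparison. It does not: per-procedure ACE, and a CUSUM built by arm from it, keep one.

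A reader might also infer that trainees certainly mix arms. The documents do not establish this. It follows only if patients are matched to trainees without regard to arm, and no matching rule is given.

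Two pieces of text are neutral and carry no weight here. In section 2, "by comparing the cases of EndolAngel assistance and no EndolAngel assistance" may refer to conditions rather than to patients. In section 3.1, the exclusion "The number of operating cases does not meet the requirement of sample size" fits either design. Finally, one test-score change per trainee is an inference, since the test, who sits it and when are not defined.

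**Conclusion.** The concern holds for the before/after test score. As documented, one of the two named primary endpoints cannot support a causal statement about AI and training, whichever way patients are matched to trainees. This rests on the readable text alone and on reading the score as one change per trainee; it needs none of the assumed figures.

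Per-procedure ACE remains a valid randomised comparison at patient level, but of a different quantity: the effect of having AI on during the case. If a trainee's AI cases improve later cases done without it, that contrast would be diluted. The documents give no basis for sizing this.

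The 13–69% power range is an illustration of what trainee allocation would cost. The documents give no trainee number, SD, ICC, alpha or power, so the range should not be read as an estimate for this trial.

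**What to change.** State the unit of allocation, say how patients are matched to trainees, and make sections 3.3, 6.1, 6.5.1 and 8.2 agree.

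**Recommended, with patient-level allocation.** Make the arm comparison of per-procedure ACE the primary analysis, in a mixed model with arm, case number, hospital and a trainee random effect. Report test scores and individual trainee CUSUM curves descriptively, and draw no conclusion from them about the effect of AI on training. This needs no extra patients. It does change the status of the named primary endpoints and gives up the causal training claim, and the amendment should say so. The possible dilution from carry-over should be acknowledged.

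**Alternative, only if trainee arms are intended and cases have not yet been randomised by patient.** Randomise trainees within hospital before their first study case, keep each in one arm and state their number. Analyse ACE with trainee as the cluster, compare the after-training test score adjusted for the before score, and restate the power. This keeps the training question but needs a protocol amendment and a trainee-level list, and on the planned cases it has lower power, especially with few trainees and hospital in the model. For cases already randomised by patient, only the first route remains.
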